5.0 RESEARCH DESIGN, METHODS AND PROCEDURES

Describe research design, methods and all study procedures

We will use two evidence-based interventions extensively tested against active and passive controls in traditional randomized controlled trials (RCTs). While overall efficacy of these interventions has been established^{7,15,16,29-31}, individuals differ in their responses. When an intervention does not initially work, clinical logic is to either extend the timeframe or prescribe a different intervention. Yet, these alternatives are seldom tested and not evidence-based. The proposed project advances beyond a traditional RCT of testing fixed “one size fits all” interventions to the sequential multiple assignment randomized trial (SMART) ³²⁻³⁷ design to build the evidence base for intervention sequencing that accounts for heterogeneity of responses. The first intervention, a printed Symptom Management and Survivorship Handbook (SMSH) with strategies for self-management of symptoms common during chemotherapy^{15,16,30} will be given to both survivor and caregiver (the dyad). SMSH strategies, if successfully enacted by the dyad, produce positive symptom responses for the survivor. However, psychological distress of the survivor or the caregiver may diminish the receipt and enactment of the SMSH strategies and also exacerbate the severity of other symptoms³⁸ which, in turn, produces poor symptom responses.³⁹ Research by this team^{40,41} and others⁴²⁻⁴⁸ has documented dyadic effects where survivors’ psychosocial distress impacts that of the caregiver and vice versa.⁴⁹ The survivor’s and caregiver’s distress exhibit similar trajectories. Therefore, the second intervention tested in sequencing is the 8-week telephone interpersonal counseling intervention (TIP-C) to manage psychological distress of the dyad.^{8,50} This project will determine which dyads require which intervention sequence: SMSH alone, SMSH alone stepped up with TIP-C based on demonstrated needs after giving SMSH alone 4 weeks of time, or a combined TIP-C+SMSH for the first 8 weeks then SMSH alone for 4 weeks. Dyads will be initially randomized to either SMSH alone or TIP-C+SMSH (Figure 1). If the survivor’s depression or anxiety does not respond to SMSH alone at week 4, dyads will be re-randomized to the TIP-C+ SMSH or continue with SMSH alone. Outcome data will be collected at baseline, weeks 13 (post-intervention) and 17 (follow-up). Brief assessments during weeks 1-12 will track any change in the dyad’s symptoms, intervention receipt, enactment and fidelity. Assessments and interventions are telephone-delivered in English or Spanish based on participant preference, as done in past studies.^{8,50,51}

Design. We selected the SMART design (Figure 1) for this study over alternative designs (e.g., implementation designs) because the SMART design allows a precision or personalized approach to determine the right treatment at the right dose with the right sequence for the right survivor-caregiver dyad. SMART designs, although newer, show promise in developing the sequences of evidence-based interventions for more efficient and individualized patient- and caregiver-centered care. We will use findings from this study to create an algorithm for clinically meaningful decision making about symptom management for survivors and their caregivers to be tested in future implementation/dissemination studies. We will recruit 298 cancer survivors undergoing chemotherapy, targeted therapy, or hormonal therapy for a solid tumor at the NCI designated University of Arizona Comprehensive Cancer Center (UACC, Tucson and Phoenix locations) and at Arizona community oncology settings. The survivors will be screened for moderate or severe depression and/or anxiety prior to enrollment and identify the informal caregivers who will participate in the study. Following enrollment, informed consent and baseline interview of both survivor and caregiver, the dyad will be randomly assigned to either: 1) SMSH alone or 2) TIP-C+SMSH for 8 weeks followed by continued SMSH alone for 4 weeks. During 12 weeks following initial randomization, all participants will receive weekly telephone contacts to assess symptoms, deliver the assigned intervention and assess its enactment and fidelity. After the initial 4 weeks in the SMSH alone group, the survivor’s response to the intervention will be determined. If the survivor responds (defined as a reduced score on depression and/or anxiety) (See C9a. Primary Outcomes), the dyad will continue with the SMSH alone for 8 more weeks. If the survivor is a non-responder (defined as no improvement or a worsening score for depression and/or anxiety), the dyad will be re-randomized to either continue with SMSH alone for 8 more weeks, or add 8 weeks of TIP-C. The rationale for using the survivor’s response as the criterion for re-randomization is from the extensive evidence of interdependence in survivor and caregiver outcomes presented, and on the caregiver’s focus on the survivor’s outcomes. The rationale for timing of the assessment of response and re-randomization to add the TIP-C intervention after 4 weeks is based on past testing of the SMSH,^{15,16,30} where median time to response on psychological distress ranged from 14 to 24 days. Post-intervention and follow-up telephone assessments are at weeks 13 and 17.

Analytic Methods

Data management. All data will be entered into the secure web-based database. Quarterly quality assurance checks of the data will be performed by the RA supervised by [name]. De-identified data will be transferred into SAS 9.4 for analyses. The distributions of outcomes and potential covariates will be assessed, outliers will be investigated by inspecting the residuals, and models described below will be fit with and without outliers to examine their influence on the results.

Attrition Analyses and Handling of Missing Data. We will compare dyadic characteristics of those who completed the study to those who did not within their designated group to inform the generalizability of findings. Attrition will also be compared between each pair of randomized groups. The regression techniques described below allow for missing at random (MAR) mechanism.²⁶⁴ If patterns of missing data indicate potential not missing at random (NMAR) mechanisms, then models describing missing mechanisms will be considered (e.g., pattern-mixture models),^{265,266} and sensitivity analyses will investigate the robustness of the results.

Primary Analysis. Primary analyses will follow the intent to treat approach.

Aim 1, Hypothesis 1: Dyads initially randomized to the TIP-C+SMSH will report lower depression, anxiety, and summed severity of other symptoms at weeks 1-12, 13, and 17, and lower unscheduled health services use, higher self-efficacy and social support, and lower caregiver burden at weeks 13 and 17 as compared to those initially randomized to the SMSH alone. This hypothesis will be tested using statistical model #1 that relates repeated measures of the survivor or caregiver outcome y (one at a time) to the group assignment variable xx_1 , outcome at baseline xx_2 , time entered as a class variable to model potentially non-linear patterns, and other covariates. For normally distributed outcomes, this model will be fit as a linear mixed effects model (LME). Generalized linear mixed effects (GLME) modeling will be used if outcome is not normally distributed and cannot be normalized using transformations. For health service use, statistical model #1 will be implemented as a GLME model with Poisson distributed errors, or as a zero-inflated Poisson or negative Binomial model based on the distribution of the counts of different health services uses. Each type of health services use (e.g., hospitalizations, ED visits) will be analyzed separately. The explanatory variables including study group will be evaluated as predictors of zero inflation (whether or not the count is zero), and also as predictors of the magnitude of the count when it is not zero. The main effects of the group variable xx_1 will be tested.

Aim 2, Hypothesis 2: Dyads where survivors do not respond to the SMSH alone during weeks 1-4 and have TIP-C added during weeks 5-12, will report lower depression, anxiety, and summed severity of other symptoms at weeks 5-12, 13, and 17, and lower unscheduled health services use, higher self-efficacy and social support, and lower caregiver burden at weeks 13 and 17 as compared to those who are re-randomized to continue with the SMSH alone. The strategy described under the analyses for Aim 1 will be implemented for the repeated outcome measures during weeks 5-12 and weeks 13 and 17 that will be related to group assignment from the second randomization, symptom severity during week 4, time, and covariates.

Mediation analyses for Aims 1 and 2. To test for mediation, the study group will be treated as the independent variable, and each of the potential mediators (one at a time) will be tested for their effect on the symptom outcome variable at weeks 13 and 17, with the baseline measure of that respective symptom outcome variable treated as a covariate. Caregiver burden will be tested only at the individual level, but social support and self-efficacy will be tested at the individual and dyadic levels. We will use a bias corrected bootstrapping analytic strategy^{267,268} based on 5000 bootstrap samples to estimate confidence intervals around the indirect effect of study group on the outcome variable, through the mediator. To establish mediation, the 95% confidence interval around the indirect effect must not include 0.

Aim 3 examines the dyadic interdependence in outcomes between survivors and caregivers. This interdependence will be modeled and tested with the actor-partner interdependence mediation model (APIMem)²⁶⁹ in structural equation modeling. The APIMem estimates three classes of effects: actor effects (e.g., person A independent variable (IV) \rightarrow person A dependent variable (DV)), caregiver (partner) effects (e.g., person A IV \rightarrow person B DV), and mediation effects (e.g., person A IV \rightarrow person B Mediator \rightarrow person A DV) in an omnibus model. These models will specify correlations between the survivors' and caregivers' IVs as well as covariances between the error terms of the mediators and outcome variables, recognizing that these residuals will covary between dyad members due to unmeasured common causes. We will fit both a saturated version of the model in which all actor, partner, and mediation effects are free to vary and compare that with a

constrained model in which the effects for one dyad member are constrained equal to the corresponding effects of the other dyad member. The χ^2 difference test will determine whether the more parsimonious constrained model or the unconstrained model will be interpreted. This test will also indicate whether the effect for survivors is significantly different from that of caregivers. These models will test whether baseline to week 17 changes in survivors' outcomes of depression, anxiety and summed severity of other symptoms are mediated by the intervening (week 13) state or caregivers' outcomes or potential covariates.

Exploratory Aim 4. The dyadic characteristics of responders will be compared to those of non-responders using t-tests, chi-square or Fisher's exact tests. Characteristics found to differ, along with mediators and other covariates listed in section C9d will be further considered as potential future tailoring variables. The decision rule (dd_1, dd_2) specifying the first and second intervention to achieve optimal outcome will be using the Qlearning optimization method^{258,270-272} implemented in SAS PROC QLEARN.^{273 274} The Q-learning algorithm proceeds backwards from the last decision to the first. Two Q-functions will be considered. The function $QQ_2(HH_2) = EE[YY_2|HH_2]$ is the expectation of the second stage outcome YY_2 given history after 2 stages, denoted by HH_2 : dyadic characteristics, outcomes observed during weeks 1-12, 13 and 17, and interventions received. The function $QQ_1(HH_1) = EE[YY_1 + \max QQ_2(HH_2)]$ uses history through the first intervention stage HH_1 . The conditional expectations in the Q-functions will be estimated from regression analyses for the primary outcomes, and the optimal decision rules will be found using backward induction by maximizing these functions.^{275,276} The product of this analysis will be identification of tailoring variables to operationalize the decision rules of selecting the optimal first intervention and switching from SMSH alone to TIP-C+SMSH. These personalized decision rules can then undergo testing in a future confirmatory RCT.

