Sample size and power considerations. To determine sample size, we started at the right of the schematic in Figure 1 (the second randomization) and moved from right to left to determine the needed number of consenting dyads. To power the comparisons on primary outcomes for the groups created by the second randomization (Aim 2), we used the effect size of Cohen’s $d=0.39$ (adjusted for baseline), the smallest seen in the preliminary data for TIP-C against an educational intervention (Table 1) to conservatively estimate sample size requirements. We further adjusted this effect size for the reduction in error variance due to 10 repeated measures of primary outcomes. In past studies, Pearson correlation coefficients between pairs of repeated measures of depression, anxiety and summed severity of other symptoms ranged from $r=0.36$ to 0.77, resulting in the range of the adjusted effect sizes from $d=0.54$ to 0.84. Using the smallest adjusted $d=0.54$, the required sample size is 60 per group created by the second randomization, for power of .80 or greater in two-tailed tests at the 0.05 level of significance.

Moving from left to right in Figure 1 (schematic), 120 dyads from two groups created by the second randomization will be non-responders to the SMSH alone. From past work, response rate to the SMSH on depression and anxiety was approximately 30%,²²⁸ therefore 120 non-responders will be 70% of 172 randomized to the SMSH alone in the first randomization. The comparison of these 172 to 60 dyads allocated to the TIP-C+SMSH in the first randomization will have power of 0.95 to detect the effect size of 0.54 (adjusted for the repeated measures) in testing the hypothesis associated with Aim 1. The tests of mediation and interdependence effects in Aim 3 will have an even greater power because of further reduction in error variance. Aim 4 is exploratory, thus formal power considerations are not applicable. In summary, the total

required post-attrition sample size for all specific aims is N=232. To account for 22% attrition based on past work, we will need 298 dyads to consent.

Recruitment and retention of participants.

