Response will be assessed using the depression and anxiety items of the GSDS administered during weekly calls to survivors. Based on the inclusion criteria and established and validated symptom cut points,²²⁴ survivors will enter with moderate or severe depression and/or anxiety (one symptom or both). The cut-points are anchored in how much symptoms are distressing the participant by interfering with enjoyment of life, social relationships, and general daily activities. Participants indicate the severity/distress from 1 to 10. For depression, the mild category corresponds to a severity score of 1, the moderate category corresponds to scores 2-3, and scores of 4-10 fall into the severe category. For anxiety, the mild category is

severity of 1-3, the moderate category corresponds to scores 4-5, and the severe category is 6-10. Survivors who start at severe or moderate on depression and/or anxiety symptoms at intake and end at a lower category by the week 4 observation will be called **responders to the intervention**.²²⁸ If a symptom was mild at intake, symptom response would not be applicable. Because responders demonstrate substantial improvement anchored to symptom distress after 4 weeks, responders will continue with the SMSH only intervention for another 8 weeks. **Non-responders to the intervention** are survivors who do not respond on either or both symptoms.^{224,251,252} Non-responding survivors and their caregivers will be re-randomized to either continue with the SMSH alone for 8 weeks to give it additional time or add TIP-C for 8 weeks to rigorously test the value added by the more intensive intervention in Aim 2. Total intervention time is 12 weeks.

Caregivers' and survivors' depression and anxiety. PROMIS-short forms 8: depression and anxiety²⁵³⁻²⁵⁶ will be administered at baseline, 13 and 17 week telephone interviews to provide greater detail and precision in the measurement of these outcomes, as compared to single GSDS items administered in weekly calls. We chose 8-item short forms to minimize respondent burden while maintaining measurement precision.

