Scientific Rigor and Transparency. The scientific rigor of this study is ensured by the randomized design, complete inclusion/exclusion criteria defining the population to which findings would be generalizable, reproducible manualized protocol for the interventions, tracking of intervention fidelity, dose, receipt and enactment, use of measures with solid evidence of reliability and validity, blinding of data collectors, transparent assessment and statistical analysis plans including attention to biases and the missing data.

Sex as a biological variable. We will consider survivors' and caregivers' sex as covariates in all analyses. Past research indicates that the survivor-caregiver relationship (spouse/partner versus other) is a key factor that may influence outcomes^{62,165} for the dyad over and above sex. Relationship will be controlled in randomization and considered along with sex as a covariate and potential future tailoring variable.

Analytic Methods

Data management. All data will be entered into the secure web-based database. Quarterly quality assurance checks of the data will be performed by the RA supervised by [name]. De-identified data will be transferred into SAS 9.4 for analyses. The distributions of outcomes and potential covariates will be assessed, outliers will be investigated by inspecting the residuals, and models described below will be fit with and without outliers to examine their influence on the results.

Attrition Analyses and Handling of Missing Data. We will compare dyadic characteristics of those who completed the study to those who did not within their designated group to inform the generalizability of findings. Attrition will also be compared between each pair of randomized groups. The regression techniques described below allow for missing at random (MAR) mechanism.²⁶⁴ If patterns of missing data indicate potential not missing at random (NMAR) mechanisms, then models describing missing mechanisms will be considered (e.g., pattern-mixture models),^{265,266} and sensitivity analyses will investigate the robustness of the results.

Primary Analysis. Primary analyses will follow the intent to treat approach.

Aim 1, Hypothesis 1: Dyads initially randomized to the TIP-C+SMSH will report lower depression, anxiety, and

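### For outcomes measured only at the week 13 and 17 interviews, the planned model drops anyone with neither interview and leaves the weekly GSDS scores unused, so its missing-at-random assumption is narrower than it needs to be and is not assured

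*Combined protocol and SAP*

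**What the plan says.** Section 5.0 (Analytic Methods), repeated in Section 8.0, states "The regression techniques described below allow for missing at random (MAR) mechanism" and "Primary analyses will follow the intent to treat approach". It will compare completers with non-completers within group and compare attrition between each pair of randomised groups. If the patterns suggest data not missing at random, pattern-mixture models will be considered and sensitivity analyses run. Multiple imputation, joint models and auxiliary variables are not mentioned.

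Model #1 "relates repeated measures of the survivor or caregiver outcome y (one at a time) to the group assignment variable", with the baseline value, time as a class variable and other covariates. Aim 2 uses the same strategy with week-4 symptom severity in the model.

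Section 6.0 sets the schedule:
- GSDS depression, anxiety and the sum of 13 other symptoms: every weekly contact and every interview, for both dyad members.
- PROMIS depression and anxiety, placed under Primary outcomes: these "will be administered at baseline, 13 and 17 week telephone interviews to provide greater detail and precision in the measurement of these outcomes".
- PROMIS self-efficacy, PROMIS social support, caregiver burden and health services use: interviews only.
- Self-efficacy for symptom management: a GSDS item, so part of the weekly instrument.

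No missing-data method is named for the bootstrap mediation analyses or the Aim 3 structural equation models.

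**The concern.** A mixed model uses everyone who has at least one response value. For a weekly outcome, someone who leaves in week 7 still contributes several rows. For an interview-only outcome the same person contributes none, because baseline enters as a covariate and not as a response. The analysis then rests on those with a week-13 or week-17 interview, and the weekly symptom course before departure plays no part.

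At stake is the group effect on PROMIS depression and anxiety, the mediators, caregiver burden and health services use. Reasons for leaving could plausibly differ by arm: TIP-C+SMSH involves a 40-minute weekly call for 8 weeks and SMSH alone a call of about 10 minutes (Section 7.0). If people with worsening symptoms leave one arm and not the other, the remaining groups are no longer comparable given baseline, and data already collected could help correct this.

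**Working it through.** **1. The plan's own figures (Section 4.0).**
- Enrolment: 232 / (1 − 0.22) = 297.4, so 298. Reproduced.
- Aim 1 power, 172 v 60 at d = 0.54: Φ(0.54 / √(1/172 + 1/60) − 1.96) = Φ(3.60 − 1.96) = 0.95. Reproduced.
- Expected loss: 298 − 232 = 66 dyads (66/298 = 22.1%). The split before and after week 13 is not given, so anywhere from 0 to 66 dyads could leave the interview-only models entirely.

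**2. Which outcomes are exposed.** The Aim 2 sample size uses a "reduction in error variance due to 10 repeated measures of primary outcomes". Weeks 5–12, 13 and 17 make 8 + 1 + 1 = 10 measures, which only the GSDS outcomes have. The powered comparison therefore keeps early leavers. The exposed outcomes are those with two post-baseline measures.

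**3. Size of the bias.** Large-sample simulation.
- From the documents: effect −0.39 SD (Section 4.0), 22% attrition.
- Assumed: correlation of baseline with later scores 0.5; last weekly GSDS with the interview outcome 0.5 or 0.7; week 4 with last weekly 0.7 and with the outcome 0.5; 10% or 22% lost before week 13, at equal rates in both arms.
- Loss model: logit P(lost) = a + b × last weekly GSDS, with b = ln 2 (odds ratio 2 per SD), 0, or −ln 2.

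Estimated effect (truth −0.39). Each range runs over the two correlations:

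| Loss depends on weekly GSDS | Share lost | Group + baseline (Aim 1 form) | Group + baseline + week 4 (Aim 2 form) | Weekly GSDS in imputation |
|---|---|---|---|---|
| same way in both arms | 10–22% | −0.39 | −0.39 | −0.39 |
| in SMSH alone only | 10% | −0.37 to −0.36 | −0.38 to −0.37 | −0.39 |
| in SMSH alone only | 22% | −0.35 to −0.33 | −0.38 to −0.35 | −0.39 |
| opposite in the two arms | 10% | −0.36 to −0.33 | −0.38 to −0.35 | −0.39 |
| opposite in the two arms | 22% | −0.32 to −0.26 | −0.36 to −0.30 | −0.39 |

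Two variations:
- With a baseline correlation with the weekly scores of 0.4 in place of 0.5, the −0.33 in the one-arm, 22% row becomes −0.32.
- If week-4 severity replaces baseline in Aim 2, which the text allows, the ranges over 10–22% loss are −0.38 to −0.34 (one arm) and −0.37 to −0.29 (opposite).

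**4. A second set of assumptions.** One common correlation across all measures (0.36 or 0.77, the ends of the range in Section 4.0), slope 1 per SD on the mean of weeks 5–12, and no week-4 term. Loss depending on baseline only, or alike in both arms: about 0% bias. SMSH alone only: the effect shrinks 5–8% at 10% loss and 10–16% at 22%. Opposite: 10–16% and 21–34%. With weekly GSDS in the imputation, bias is at most 0.002 SD.

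**5. Where the remedy stops working.** If loss at 22% depends on the unseen interview outcome itself (odds ratio 2), imputation with weekly GSDS gives −0.32 to −0.30 (one arm) and −0.25 to −0.20 (opposite). The current model with baseline gives about −0.28 and −0.17.

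**The case against.** A reader might infer that the missing-at-random and intent-to-treat statements fail outright. The documents do not support that. The plan says only that its techniques allow for missing at random. A likelihood model does so given what it contains, and the check shows no bias when loss depends on baseline, or on weekly scores alike in both arms at equal rates.

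A reader might also infer that the main hypothesis is compromised. It is not: outcomes at weeks 1–12 can only be GSDS scores, and those models retain early leavers. Nor is every mediator exposed, since the symptom-management self-efficacy item is weekly.

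Three further objections stand in part:
- The Aim 2 model already carries week-4 severity, which reduces the bias but does not remove it.
- The larger shifts need opposite loss mechanisms by arm and all 22% lost before week 13. Neither is documented.
- Imputation recovers −0.39 in step 3 because loss was generated from the variable used to impute. Someone who leaves after one call has little weekly history to use.

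The plan's safeguards do not close the gap. Section 8.0 cites past studies without differential attrition, and the plan will compare attrition between groups, but every biased row above has equal rates in both arms. The fallback for data not missing at random is conditional and unspecified. It also addresses a different problem from leaving observed data unused.

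For mediation and Aim 3 the plan is silent on missing data. A reader might infer that those models also drop early leavers, but full-information likelihood is not excluded.

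**Conclusion.** The point holds for interview-only outcomes. Anyone with neither a week-13 nor a week-17 interview leaves model #1, and the assumption is conditional on less than the trial will have observed. It is narrower than it needs to be and not assured, which is less than saying it is wrong.

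The size depends on how loss works. It is nil for a common mechanism. If loss tracks weekly GSDS differently by arm, a true −0.39 SD becomes about −0.37 to −0.32 (one arm) or −0.36 to −0.26 (opposite). With baseline and week-4 adjustment in Aim 2 it becomes about −0.38 to −0.35 or −0.38 to −0.30. These rest on the assumed correlations, an odds ratio of 2 per SD and 10–22% lost before week 13. They apply to roughly continuous scores. Health services counts have the same gap, but the SD figures do not carry over to them.

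Using the weekly scores did no worse than the current model in any scenario examined and removed the bias where loss depended on them. That makes it a worthwhile improvement to specify in advance.

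**What to change.** For PROMIS depression and anxiety, PROMIS self-efficacy and social support, caregiver burden and health services use, analyse all randomised dyads. Multiply impute weeks 13 and 17 within randomised group, with the weekly GSDS depression, anxiety and 13-symptom sum of both dyad members in the imputation model, or fit a joint mixed model. Use a count model for health services use.

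Three scores over 12 weeks for two people give 72 weekly variables, against about 60/0.78 = 77 dyads in the smaller arm. Name summaries in advance, such as the last observed value and the mean. Within SMSH alone, include response status and the second assignment.

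For the mediation and Aim 3 models, state the method: the same imputations, or full-information likelihood with these scores as auxiliary variables.

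Report the current model alongside. Retain the sensitivity analyses for data not missing at random, because step 5 shows that the weekly scores do not protect against loss driven by the unseen outcome. Report how many people have neither interview, by group.

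Cost: SAP wording, an imputation model to specify and modest programming. No new data are needed.
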